9.4.1. Imputation of endpoints data

To achieve the largest possible sample, imputation techniques will be used to impute missing data for the FAS population. Missing data on the primary efficacy endpoint will be imputed using conventional Multiple Imputations approach. The SAS® MI procedure will be employed to perform multiple imputation in order to obtain Maximum Likelihood estimates which, by definition, are unbiased under a MCAR and MAR mechanism for missing values.

The following MI procedure code will be used to perform MI with 5 imputations.

```
PROC MI data = dataset seed=s out = MIdataset n impute = 5;
VAR study_treatment carboplatin country vis1_event - vis3_event;
CLASS study_treatment carboplatin country vis1_event - vis3_event;
monotone logistic;
RUN;
```

The exact names of the variables may differ.

9.4.2. Missing data within the FAS population on secondary efficacy endpoints will be imputed using the last observation carried forward (LOCF). Primary Efficacy Endpoint

The primary efficacy endpoint “Proportion of complete responses over three cycles of chemotherapy after the start of the MEC administration” will be analyzed by means of a generalized linear model (GLIM) with logit link function, binomial distribution and with “study treatment” (NEPA + Dex or Standard of care), “carboplatin use” (yes or no) and “country” as factors, using data from the overall period of three cycles.

Moreover, the GLIM model will be parameterized with generalized estimating equations with an exchangeable working correlation matrix to take into account clustered data (i.e. three repeated measures corresponding to as many cycles of chemotherapy within each subject). Results will be reported as odds ratios with associated two-sided 95% confidence intervals and p-values.

The results will be obtained via the GENMOD procedure, using following code:

```
PROC GENMOD data = dataset;
CLASS id study_treatment carboplatin country;
MODEL complete_response = study_treatment carboplatin country / dist = bin
link = logit;
REPEATED subject = id / type = exch covb corrw;
LSMEANS study_treatment / diff exp ilink cl;
RUN;
```

The exact names of the variables may differ.

With MI the code will be modified to:

```
PROC GENMOD data = dataset;
CLASS id study_treatment carboplatin country;
MODEL complete_response = study_treatment carboplatin country / dist = bin
link = logit;
REPEATED subject = id / type = exch ecovb;
LSMEANS study_treatment / diff exp ilink cl;
ODS OUTPUT GEEEmpPEst=parms_est;
RUN;

PROC MIANALYZE parms(classvar = LEVEL)=parms_est;
```

```

CLASS study_treatment carboplatin country;
MODELEFFECTS Intercept study_treatment carboplatin country;
ODS OUTPUT ParameterEstimates = combined_parms;
RUN;

```

The exact names of the variables may differ.

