9.2. Determination of Sample Size

A sample of 410 randomised subjects, each scheduled to be measured 3 times/cycles, achieve a 80% power when using a two-sided Wald test from a GEE analysis to test whether the proportion of Complete response expected in the Test group (71%) differs from that expected in the Control group (60%) at a significance level of 0,050. The subjects are randomly split between a Test group and a Control group, with 50% of the subjects assigned to the Test group. The measurements of each subject will be made at the following times/cycles expressed as proportions of the total study time: {0%; 50%; 100%}. Missing values are assumed to occur completely at random (MCAR) or at random (MAR). These missing value proportions will be combined to form the pairwise observant probabilities using the Independent method. The anticipated proportions missing at each measurement time/cycle are {0%; 7.5%; 15%}. Based on these attrition rate scenario, a sample of 348 completer subjects is expected. The correlation between observations on the same subject is assumed to be 0.5 (ballpark estimate). All computations are performed using PASS 14 software.

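### Five imputations and an unfilled seed leave avoidable Monte Carlo noise in the primary test, which matters only when the p-value is near 0.05

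*SAP*

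**What the plan says.** SAP 9.4.1 states: "Missing data on the primary efficacy endpoint will be imputed using conventional Multiple Imputations approach". It then fixes the number of imputations: "The following MI procedure code will be used to perform MI with 5 imputations". The code line begins "PROC MI data = dataset seed=s", so a seed argument is present but holds no number. The imputation model is a monotone logistic sequence on "VAR study_treatment carboplatin country vis1_event - vis3_event". The note under the code allows variable names to change and does not mention the seed.

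The primary-endpoint text that follows analyses the imputed data by a logit model fitted with "generalized estimating equations with an exchangeable working correlation matrix to take into account clustered data", pooled with PROC MIANALYZE. SAP 9.2 sizes the trial to "achieve a 80% power when using a two-sided Wald test from a GEE analysis", at a significance level of 0.05. SAP 9.1.2 has p-values rounded to three decimals.

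Protocol 8.4 leaves the details of multiple imputation to the SAP. Neither document gives a seed value, a rule for setting one before database lock, or a check on Monte Carlo error. SAP 9.1.5 requires double programming of the primary analysis. The trial is open label (Protocol 3.1), and SAP 9.9 lets each country summarise its own data, including endpoint frequencies by arm, before the final analysis.

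**The concern.** Multiple imputation draws the missing values at random, so the pooled estimate and its p-value depend on the draws. The dependence shrinks as the number of imputations m grows. Few imputations are usually defended on efficiency, meaning average precision over repeated trials. The question here is different: for one locked data set, how far does the p-value move when only the seed changes?

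This trial has one confirmatory test at two-sided 0.05. If the result lies close to that line, five imputations may not settle which side it falls on. An unfilled seed adds a second, smaller issue: the choice that decides the draws is not fixed in advance, although summaries by arm may already have been seen.

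**Working it through.** **1. The plan's sample size, reproduced.** Inputs from SAP 9.2: 71% v 60%, 1:1 allocation, three cycles, correlation 0.5, missing 0/7.5/15%, pairwise probabilities by the Independent method, two-sided 0.05, power 80%.
- Observed proportions are 1, 0.925 and 0.85, with sum 2.775.
- f = Σ(pairwise observed probability × correlation) / (Σ observed)² = 5.336 / 7.701 = 0.693.
- Log odds ratio = 0.490; 1/(0.71×0.29) + 1/(0.60×0.40) = 9.023.
- n per arm = 0.693 × (1.960 + 0.842)² × 9.023 / 0.490² = 204.5, rounded up to 205. So N = 410, with 80.1% power. Completers: 410 × 0.85 = 348.5.

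This matches the stated 410 and 348, so the attrition and correlation used below are those behind the plan's own figure. The expected z at the planned effect is about 2.80.

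**2. Fraction of missing information (FMI).** This was found by simulation at the planned attrition: 410 patients, beta-binomial responses with correlation 0.5, monotone dropout, sequential logistic imputation and exchangeable GEE. Over 60 simulated trials at 71% v 60%, the ratio of between-imputation to total variance averaged 0.037. The implied SD of z between seeds at m = 5 averaged 0.085 (10th to 90th percentile 0.070 to 0.099). Six countries is an assumption.

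**3. Spread of the p-value across seeds.** SD of z between seeds ≈ √(FMI/m). The limiting p is the value approached as m grows without bound. For a limiting p of 0.050 (z = 1.96), 95% of seeds lie within z = 1.96 ± 1.96 × SD.

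| FMI | m | SD of z | p in 95% of seeds |
|---|---|---|---|
| 3.7% | 5 | √(0.037/5) = 0.086 | 0.033–0.073 |
| 3.7% | 100 | √(0.037/100) = 0.019 | 0.046–0.055 |
| 2% | 5 | 0.063 | 0.037–0.066 |
| 8% | 5 | 0.126 | 0.027–0.087 |

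**4. Direct check.** Simulated data sets were each imputed 2,000 times, and the imputations were split into blocks of m pooled by Rubin's rules with a t reference. This run also assumed 20% carboplatin use, no covariate effects beyond treatment, and a true test-arm rate of 69% to obtain data sets near the threshold. Eight data sets at the planned missingness had a limiting p of 0.049 to 0.059.

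| m | SD of p | p in 95% of seeds | Seeds on the other side of 0.05 from the limiting p |
|---|---|---|---|
| 5 | 0.0115 | 0.036–0.081 | 34% |
| 20 | 0.0055 | 0.045–0.065 | 25% |
| 50 | 0.0032 | 0.048–0.060 | 17% |
| 100 | 0.0022 | 0.050–0.058 | 11% |

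These ranges sit a little higher than in step 3 because most of the eight limiting p-values are above 0.05. At half the planned missingness (FMI 2.0%) the m = 5 range is 0.038–0.069; at double (FMI 8.1%) it is 0.025–0.096. For data sets with a limiting p of about 0.03, only about 3% of seeds cross 0.05 at m = 5.

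**5. How often the verdict changes.** Integrate, over the distribution of z at the planned effect (centre 2.80, SD 1), the chance that seed noise carries z across 1.96. This is approximately 2 × SD/√(2π) × φ(2.80 − 1.96). With m = 5: 0.798 × 0.086 × 0.28 = 0.019. With m = 100: 0.798 × 0.019 × 0.28 = 0.004. With no treatment effect and m = 5 it is about 0.4% per tail.

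**6. What m = 5 does not cost.** Relative efficiency is 1/(1 + 0.037/5) = 0.993.

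**The case against.** The strongest reply is that this seldom matters. Five imputations with about 4% missing information are unbiased and about 99% efficient. In about 98% of trials at the planned effect the verdict is the one that unlimited imputations would give. Sites also complete missing diary, MAT and FLIE answers with the patient (Protocol 3.6.3), which may reduce item-level gaps, though not dropout. All of this stands, and it keeps the point minor.

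A reader might infer that the primary p-value cannot be reproduced. The documents do not support that. The code carries a seed argument, the final program must hold a number there, and SAP 9.1.5 has a second programmer repeat the analysis. What is missing is a seed fixed in advance, so that the p-value follows from the SAP alone.

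A reader might also infer that the seed could be picked to suit the result. Nothing in the documents suggests this, and the SAP 9.9 summaries are descriptive, without testing or imputation. They show only that arm-level outcomes may be seen while the seed is open.

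Finally, 100 is not a unique answer. With m = 50 the SD of p near 0.05 is already about 0.003, and even m = 100 leaves some reversals when the limiting p is almost exactly 0.05. A stated Monte Carlo tolerance is a sounder basis than a bare number.

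**Conclusion.** The point holds as a small improvement to the primary analysis. Near the threshold the effect of the seed is clear: a limiting p of 0.050 is reported between about 0.033 and 0.073 in 95% of seeds with m = 5, against 0.046 to 0.055 with m = 100. Away from the threshold it fades quickly. Averaged over trials at the planned effect, it changes the verdict in about 2%, falling to about 0.4% with m = 100. Validity and power are not in question.

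The size depends mainly on how much is missing, hence the ranges for FMI of 2% and 8%. It also rests on monotone dropout, six countries, 20% carboplatin use and no covariate effects beyond treatment, none of which the documents state as planning values. The unfilled seed alone would be little more than a missing detail; the low m is the part that a better choice improves.

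**What to change.** Before database lock, change two entries in SAP 9.4.1:

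- Raise the number of imputations from 5 to about 100, or state the target instead: enough imputations to hold the Monte Carlo SD of the p-value near 0.05 at about 0.002.
- Replace the placeholder with a numeric seed, and state the record order of the input data set, so that both programmers obtain the same p-value from the SAP alone.

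The seed removes discretion, and the larger m removes most of the noise; each does a separate job. The estimand, imputation model, analysis model and sample size stay as they are. The cost is a minor SAP version update with its approval, and trivial computing time.

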### 8.2. Sample Size Analysis

A sample of 410 randomised subjects, each scheduled to be measured 3 times/cycles, achieve a 80% power when using a two-sided Wald test from a GEE analysis to test whether the proportion of Complete response expected in the Test group (71%) differs from that expected in the Control group (60%) at a significance level of 0,050. The subjects are randomly split between a Test group and a Control group, with 50% of the subjects assigned to the Test group. The measurements of each subject will be made at the following times/cycles expressed as proportions of the total study time: {0%; 50%; 100%}. Missing values are assumed to occur completely at random (MCAR) or at random (MAR). These missing value proportions will be combined to form the pairwise observant probabilities using the Independent method. The anticipated proportions missing at each measurement time/cycle are {0%; 7.5%; 15%}. Based on these attrition rate scenario, a sample of 348 completer subjects is expected. The correlation between observations on the same subject is assumed to be 0.5 (ballpark estimate). All computations are performed using PASS 14 software.

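### The imputation step for the primary endpoint (SAP 9.4.1) covers drop-out only and gives no valid handling for a missing cycle followed by an observed one

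*SAP*

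**What the plan says.** Protocol 8.4 (Efficacy Analysis) has missing primary-endpoint data multiply imputed and leaves the details to the SAP. SAP 9.4.1 supplies them: a PROC MI step with 5 imputations. Its variable list runs treatment, carboplatin use, country and then the outcomes `vis1_event` to `vis3_event`, and its only imputation statement is "monotone logistic". The note under the code allows only variable names to change. SAP 9.1.3 (Missing Data) refers back to this section and adds nothing.

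The sample-size text (protocol 8.2, repeated in SAP 9.2) plans for "A sample of 410 randomised subjects, each scheduled to be measured 3 times/cycles", with 0%, 7.5% and 15% missing at cycles 1, 2 and 3. These are turned into "pairwise observant probabilities using the Independent method". The same paragraph then expects 348 completers.

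The outcome data come from paper. Under protocol 3.6.3, each cycle has its own MAT and diary, taken home and returned at the next visit. SAP 9.4 takes vomiting for the acute, delayed and overall phases from the MAT, and rescue medication is recorded in the diary and eCRF (protocol 3.4.3). SAP 9.9 limits the primary endpoint in the early country summaries to patients treated in all three cycles with complete MAT and diary information, so incomplete forms are foreseen.

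**The concern.** A monotone sequence imputes cycle 2 from cycle 1, then cycle 3 from cycles 1 and 2. It is defined only when an outcome is observed whenever a later one in the list is observed. A patient with cycle 1 observed, cycle 2 missing and cycle 3 observed falls outside it. The SAP has no fully conditional step, no preliminary step to make the pattern monotone, and no rule for such a patient.

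At stake is the pre-specification of the single confirmatory analysis. When the first such patient appears, someone must decide whether to discard the later observed cycle, leave the gap unimputed or adopt another method. The trial is open label, and SAP 9.9 lets endpoint frequencies by arm be tabulated by country before the global analysis. A method chosen at that stage could be challenged as influenced by the data.

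**Working it through.** **Inputs** (SAP 9.2, protocol 8.2): N = 410, 1:1; response 71% against 60%; two-sided alpha 0.05; power 80%; within-patient correlation 0.5; proportions observed d = (1, 0.925, 0.85).

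**1. Reproduce the planned N.** For a GEE Wald test on the log odds ratio,

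N = (1.960 + 0.842)² × V × F / (log OR)²

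- log OR = ln(0.71/0.29) − ln(0.60/0.40) = 0.490
- V = 1/(0.5 × 0.71 × 0.29) + 1/(0.5 × 0.60 × 0.40) = 18.05
- F = [Σd_j + 2 × 0.5 × Σd_jk] / (Σd_j)², with Σd_j = 2.775

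Independent pairs (d_jk = d_j × d_k): Σd_jk = 0.925 + 0.85 + 0.786 = 2.561; F = 5.336/7.701 = 0.693; N = 408.9, and power at 410 is 80.1%. The plan's figure reproduces.

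Drop-out pairs (d_jk = the smaller of the two): Σd_jk = 0.925 + 0.85 + 0.85 = 2.625; F = 5.400/7.701 = 0.701; N = 413.8, and power at 410 is 79.6%. The choice barely affects N.

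**2. Patterns implied by each reading, in 410 patients.**

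| Cycles 1, 2, 3 | Independent | Drop-out only |
|---|---|---|
| all observed | 0.925 × 0.85 = 0.786 → 322.4 | 0.85 → 348.5 |
| cycle 3 missing | 0.925 × 0.15 = 0.139 → 56.9 | 0.075 → 30.75 |
| cycle 2 missing, cycle 3 observed | 0.075 × 0.85 = 0.06375 → 26.1 | 0 |
| cycles 2 and 3 missing | 0.075 × 0.15 = 0.01125 → 4.6 | 0.075 → 30.75 |

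The stated 348 completers match the right-hand column; the stated combination method matches the left. The paragraph is inconsistent with itself.

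Under independence the 26 gaps are 85% of missing cycle 2 values, 26.1/92.25 = 28% of all missing values (92.25 = 410 × 0.225), and 26/1,230 = 2.1% of all scheduled cycle outcomes.

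**3. Does the point need the 26?** The documents give no gap rate of their own, so take a range as an assumption. The chance of at least one such patient in 410 is 1 − (1 − r)^410:

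| Gap rate r | Expected patients | Chance of at least one |
|---|---|---|
| 0.25% | 1.0 | 64% |
| 0.5% | 2.1 | 87% |
| 1% | 4.1 | 98% |
| 2% | 8.2 | >99.9% |

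One such patient is enough to make the data set non-monotone.

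**4. Upper bound on power.** If all 26 gap patients were lost, about 383.9 would remain, with d = (1, 0.988, 0.840) and F = 5.495/7.996 = 0.687. Power is then 77.8% against 80.1%. This is a worst case, because GEE could still use those patients' observed cycles.

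**The case against.** The strongest reply is that the plan expects drop-out. Missingness rises by cycle, the text speaks of attrition, and 348 is 410 × 0.85. The independence wording describes only how pairs were combined for the power calculation, where it moves N by about five. Gaps are also actively prevented. Forms are checked at each visit and missing answers completed with the patient, patients are called between days 3 and 5, rescue use is also asked about at the visits (protocol 3.6.3), and sites are paid for complete data on all three cycles (protocol 14). Failure to return for visits can end participation (protocol 3.4.5), which turns missed visits into drop-out.

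Much of this stands. It rules out reading 26 as a prediction. A reader might infer that the planning text and the imputation code flatly contradict each other; the 348 completers show that the planning text points both ways. A reader might also add losses at cycle 1 and reach a larger count, but the plan states 0% missing there.

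What does not stand is that the safeguards make a rule unnecessary. They reduce item gaps but cannot exclude a lost or unreturned form from a patient who continues treatment. SAP 9.4.1 also prints the GEE code without imputation, but does not name it as a fallback.

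**Conclusion.** The point holds as a gap in pre-specification that should be fixed. The only imputation method stated for the primary endpoint is not valid for intermittent missingness, and nothing else in the protocol or SAP covers it. The number of affected patients is uncertain: none under pure drop-out, about 26 of 410 (6.4%) under independence. At an assumed gap rate of 1%, at least one is about 98% likely.

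A reader might go further and infer that the program will stop, that observed outcomes will be thrown away, or that the treatment estimate will be biased. The documents do not say what the software does with a non-monotone file, the SAP prescribes no deletion of later cycles, and no bias has been shown. The effect on power is small even in the worst case (77.8% against 80.1%). The weakness is that the choice of method would be left open until after the data are seen.

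**What to change.** Before database lock:

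1. In SAP 9.4.1, replace the monotone statement with a named method for arbitrary missing patterns, for example `fcs logistic(vis1_event vis2_event vis3_event);` on the same VAR and CLASS lists. Alternatively, pre-specify a step that first makes the pattern monotone and keep monotone logistic after it. Either is acceptable if stated in advance. FCS also lets a missing earlier cycle draw on the patient's later ones, which is useful given the assumed correlation of 0.5.
2. Correct the multiple-imputation version of the GENMOD code. As printed, it reads `dataset` rather than the imputed `MIdataset` and has no BY statement for the imputation number, so changing the imputation line alone would not complete the analysis.
3. In protocol 8.2 and SAP 9.2, reconcile the 348 completers with the independence assumption: either about 322 completers under independence, or drop-out pairs with N of about 414.

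The cost is a few lines of SAP code and one clarified sentence. No extra data are needed, and the imputation change leaves the sample size as it is.

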## Study rationale and background

Despite the availability of effective antiemetics and evidence-based guidelines, up to 40% of cancer patients receiving chemotherapy fail to achieve complete nausea and vomiting control.

Antiemetic guidelines recommendations are based on the emetogenic potential of the chemotherapy. Chemotherapy (CT) agents are divided in Highly, Moderately, Low and Minimally Emetogenic potential (HEC, MEC, LEC, MiE).

In addition to type of chemotherapy, several patient-related risk factors can increase the risk of CINV. Currently, there is limited consensus surrounding the most relevant patient risk factors that may predict the risk of CINV. Based on a recent study by Dranitsaris et al. (Dranitsaris et al. Ann Oncol. 2017 Jun 1; 28(6):1260-1267.), eight (8) predictive factors have been identified and an algorithm has been developed to incorporate these factors into the optimal selection of prophylactic antiemetics:

1. nausea and/or vomiting in the prior cycle of chemotherapy
2. use of non-prescribed antiemetics at home in the prior cycle of chemotherapy
3. platinum or anthracycline-based chemotherapy
4. age < 60 years
5. expectations for (anticipating) nausea and/or vomiting
6. <7 h of sleep the night before chemotherapy
7. history of morning sickness during previous pregnancy
8. cycle of chemotherapy (A negative association between risk and number of cycles was identified where the hazard for CINV was highest in cycles 1 and 2, with a gradual decline and plateau from cycle 3 onward).

The clinical application of this prediction tool has the potential to be an important resource for clinicians and may help to enhance patient care by optimizing the use of the antiemetics in a proactive manner.

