### 8.4. Efficacy Analysis

All efficacy analyses will be performed on the FAS population. Also, analysis of the primary and secondary efficacy variables will be carried out on the Per Protocol population to assess the robustness of the findings. Safety outcomes will be analyzed on the Safety population.

CONFIDENTIAL

Confidential	MyRisk	Date: 05 February 2024
	Protocol	
	PROTOCOL NUMBER: IBA1160	Version: 5.1

The primary efficacy endpoint “Proportion of complete responses over three cycles of chemotherapy after the start of the MEC administration” will be analyzed by means of a generalized linear model (GLIM) with logit link function, binomial distribution, and with “study treatment” (NEPA + Dex or Standard of care), “carboplatin use” (yes or no) and “country” as factors. Moreover, the GLIM model will be parameterized with generalized estimating equations with an exchangeable working correlation matrix to take into account clustered data (i.e. three repeated measures corresponding to as many cycles of chemotherapy within each subject). Results will be reported as odds ratios with associated two-sided 95% confidence intervals and p-values.

The same statistical approach will be used for all the secondary efficacy endpoints except for the following outcomes “delay and/or dose reduction” which will be analyzed using a Stratified Wilcoxon Rank Sum test blocking for carboplatin use and country.

Missing data on the primary efficacy endpoint will be imputed using conventional Multiple Imputations approach. The SAS® MI procedure will be employed to perform multiple imputation in order to obtain Maximum Likelihood estimates which, by definition, are unbiased under a MCAR and MAR mechanism for missing values. Details on Multiple Imputations will be provided with the SAP.

Missing data on secondary efficacy endpoints will be imputed using last observation carried forward (LOCF). The overall type I family-wise error rate for testing the primary and the secondary efficacy parameters is controlled at the 0.05 significance level without the need for adjustments since the study is planned with a single primary endpoint and since secondary endpoints are only supportive of primary endpoint findings. All statistical analyses will be performed using SAS version 9.4 or later.

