9.4.3. Secondary Efficacy Endpoint

The same statistical approach as for the primary endpoint (GLIM) will be used for all the secondary efficacy endpoints with the exception of the following outcomes “delay and/or dose reduction” which will be analyzed using a Stratified Wilcoxon Rank Sum test blocking for carboplatin use and country, using following code (*delay_length* can be replaced with *amount_reduction*):

```

PROC NPAR1WAY data=dataset wilcoxon;
CLASS study_treatment;
VAR delay_length;
STRATA country carboplatin;
EXACT wilcoxon;
RUN;

```

The exact names of the variables may differ.

The code will be equivalent to the one used in the analysis of primary endpoint, only changing variable from *complete_response* to variables describing the secondary endpoints:

- Complete response during the acute (0-24h), delayed phase (25-120h), overall (0-120h) and daily in each cycle
- No emetic episode during the acute, delayed and overall phase and daily in each cycle
- Number of vomiting episodes during the acute, delayed and overall phase in each cycle
- No rescue medication during the acute, delayed and overall phase and daily in each cycle
- No significant nausea (maximum MAT scale = 2) during the acute, delayed and overall phase and daily in each cycle
- No nausea (MAT scale = 0) during the acute, delayed and overall phase and daily in each cycle
- Complete protection (no emetic episode, no rescue medication and no significant nausea) during the acute, delayed and overall phase and daily in each cycle
- Nausea and Vomiting-related quality of life indicators (through the Functional Living Index Emesis scale)

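### Per-cycle overall complete response is filled by multiple imputation as the primary endpoint but by LOCF as the first secondary endpoint; both should use the primary's imputed data sets

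*SAP*

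**What the plan says.** Protocol 3.5 defines the primary endpoint as complete response (no emesis, no rescue) during 0-120 h over three cycles. SAP 9.4.2 models it by GEE with three repeated values per patient, one per cycle. For gaps, SAP 9.4.1 states: "Missing data on the primary efficacy endpoint will be imputed using conventional Multiple Imputations approach".

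The first secondary endpoint in SAP 9.4.3 is "Complete response during the acute (0-24h), delayed phase (25-120h), overall (0-120h) and daily in each cycle". Its overall component is the same per-cycle variable. SAP 9.4 puts both analyses in the FAS, and SAP 9.4.3 says of the secondary model: "The code will be equivalent to the one used in the analysis of primary endpoint, only changing variable".

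The secondary endpoints get a different rule. The SAP sentence, printed in the heading line of 9.4.2, reads "Missing data within the FAS population on secondary efficacy endpoints will be imputed using the last observation carried forward (LOCF". Protocol 8.4 has the same: "Missing data on secondary efficacy endpoints will be imputed using last observation carried forward (LOCF". SAP 9.1.3 names both methods and points back to 9.4.1. SAP 10.1 lists Table 14.2-1 for the primary result and Table 14.2-2 for complete response by phase and day. Multiple imputation is justified by its behaviour under MCAR and MAR; LOCF is given no justification.

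**The concern.** A patient with no cycle-3 data could be a complete responder in some or all of the primary's imputed data sets and a failure in the LOCF data, or the reverse. The secondary results are meant to support the primary one, yet for this variable they would not reconcile with it.

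LOCF is also the weaker rule here. It assumes that a patient's response does not change after the last observed cycle. The protocol's rationale, citing a prediction study, says that "the hazard for CINV was highest in cycles 1 and 2, with a gradual decline and plateau from cycle 3 onward", and the risk score subtracts 5 points for a second cycle and 6 from the third. SAP 9.2 allows MAR dropout. Chemotherapy discontinuation due to CINV is itself an endpoint, so loss after a failed cycle is foreseeable. The trial is open label, so loss could differ by arm.

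**Working it through.** **1. Inputs and the plan's own figure.** From SAP 9.2: 410 patients, 1:1; 71% v 60%; correlation 0.5; missing 0%, 7.5%, 15%, pairs combined as independent; 80% power; "two-sided Wald test from a GEE analysis" "at a significance level of 0,050".

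- Observed fractions 1, 0.925, 0.85 sum to 2.775. The sum of products over ordered pairs is 2 × (0.925 + 0.85 + 0.78625) = 5.1225.
- f = (2.775 + 0.5 × 5.1225) / 2.775² = 5.336 / 7.701 = 0.693.
- Log OR = ln[(0.71/0.29)/(0.60/0.40)] = ln 1.632 = 0.490.
- n per arm = (1.960 + 0.842)² × [1/(0.71 × 0.29) + 1/(0.60 × 0.40)] × 0.693 / 0.490² = 7.849 × 9.023 × 0.693 / 0.240, about 204.5, so 205 per arm and **N = 410** (power 80.1%). The stated size is reproduced, and 410 × 0.85 = 348.5 matches the 348 completers.

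**2. How many values are affected.** 410 × 0.075 = 30.75 at cycle 2 and 410 × 0.15 = 61.5 at cycle 3. Together that is 92.25 of 3 × 410 = 1,230, or 7.5%. None is expected at cycle 1.

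**3. What LOCF does to the estimates.** The simulation used correlated binary responses (correlation 0.5), monotone dropout, carry-forward from the previous cycle, and 3 million patients per arm. Attrition is the SAP's unless stated. The trends, the dropout ratio of 3 and the arm-specific dropout are assumptions, not figures from the documents. RD is the cycle-3 difference in percentage points.

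| Scenario | True RD; OR | LOCF RD; OR | Pooled OR, true / LOCF |
|---|---|---|---|
| A. Flat 71/60, MCAR | 11.02; 1.633 | 11.01; 1.633 | 1.635 / 1.634 |
| B. Flat; non-responders 3 times as likely to drop out | 11.07; 1.637 | 11.06; 1.616 | 1.637 / 1.626 |
| C. Both arms rise 5 points per cycle, MCAR | 10.93; 1.699 | 10.92; 1.679 | 1.631 / 1.625 |
| D. Effect wanes (71/68/65 v 60), MCAR | 4.98; 1.237 | 5.63; 1.273 | 1.416 / 1.435 |
| E. As C, cycle-3 dropout 10% NEPA v 20% control | 10.99; 1.704 | 11.76; 1.748 | 1.632 / 1.652 |
| F. As B, dropout 10% v 20% | 10.98; 1.631 | 12.35; 1.710 | 1.633 / 1.672 |
| G. Rise, 3 times, and 10% v 20% | 10.99; 1.704 | 13.04; 1.818 | 1.627 / 1.682 |

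Imputation from earlier cycles within arm recovered the true odds ratios to within 0.003 throughout. In B, LOCF lowers the cycle-3 rates themselves to 69.0% and 58.0% from 71% and 60%, but equally in both arms.

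A hand check of C, control arm, with half of the cycle-3 losses already gone at cycle 2: 0.85 × 65 + 0.075 × 60 + 0.075 × 55 = 63.9%, against a true 65%.

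A harsher simulation assumed no true effect, missing at cycles 2/3 of 5%/10% (NEPA) v 10%/20% (control), and 80% of dropouts following a failed cycle. It gave a false cycle-3 difference of 2.0 points (flat 60%) to 2.9 points (55/60/65%). At 60% response that makes failures (0.8/0.4)/(0.2/0.6) = 6 times as likely to drop out.

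**4. Precision and agreement at 205 per arm** (3,000 simulated trials, five imputations). In scenario A, cycle-3 power was 65.0% with LOCF, the same as with no missing data, against 57.7% with multiple imputation. The two methods fell on opposite sides of p = 0.05 in 4.0% of trials for the pooled result and 12.1% at cycle 3. With rising rates and three-fold dropout of non-responders, equal by arm, the figures were 5.1% and 13.0%.

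**The case against.** Several stronger readings are tempting, and the documents do not support them.

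- *The LOCF result is biased.* Not necessarily. The trial is sized on one rate per arm, and MCAR is allowed. In that case (A) LOCF leaves rates and odds ratio unbiased. A within-patient correlation of 0.5 rather than 1 does not change this. If rates were known to be flat, even the added precision would be legitimate; it is borrowed from that assumption and not from cycle-3 data.
- *The report will carry two conflicting results.* The primary is a pooled odds ratio, and the secondary is worded by cycle. They are the same estimate only if the pooled code is run unchanged, which SAP 9.4.3 leaves open. Otherwise they share a variable whose filled values differ. Opposite significance is uncommon for the pooled result.
- *The plan contradicts its own claim that risk falls over cycles.* That statement summarises a cited study by chemotherapy cycle. Non-naive patients are eligible, and those restarting after six months or more are scored as first cycle, so study cycle need not equal chemotherapy cycle. A trend is plausible, not established.
- *The effect is inflated by 2 to 3 points.* That needs more dropout in control than in NEPA, driven by failure. SAP 9.2 gives one attrition schedule for both arms. At 60% response the standard error of a cycle-3 difference is √(2 × 0.24/205) = 4.8 points, so 2 points is about 0.4 standard errors.

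It is also fair that protocol and SAP agree with each other, that the rule is prespecified, and that secondary endpoints are called supportive only. What remains is that one variable is filled by two rules, the weaker one without a stated reason, although the better-filled data will already exist.

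**Conclusion.** The point holds as an inconsistency of method with limited consequence. For the same patients and cycles, the primary and first secondary outputs would use different complete-response data in about 7.5% of patient-cycles, and in 15% at cycle 3.

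LOCF claims more precision than the observed cycle-3 data support, even with flat rates and MCAR. It is biased under outcome-dependent dropout, which the SAP allows, or if response changes over cycles. With equal dropout by arm, the cycle-3 odds ratio moved by at most 0.036 in the cases examined (D). A shift of about 2 points in the cycle-3 difference (13.0 v 11.0 in G; up to 2.9 with six-fold dropout) appears only under assumed unequal, failure-driven dropout.

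These sizes assume that LOCF carries the previous cycle's value forward; the documents do not say so. A reader might infer that the primary conclusion or the sample size is at risk. Neither is: the primary uses multiple imputation, and N = 410 stands.

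**What to change.** In protocol 8.4 and SAP 9.4.1-9.4.3, exempt overall-phase complete response from LOCF. Suggested wording:

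> Per-cycle complete response in the overall phase will be tabulated and modelled from the imputed data sets created for the primary analysis, with estimates combined by Rubin's rules. LOCF results for this variable will be labelled as a sensitivity analysis.

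For the other binary per-cycle secondary endpoints, prefer multiple imputation of the components (emesis, rescue, nausea), and derive complete response and complete protection afterwards. Separate imputation of each endpoint should be avoided. Six binary endpoints over three phases and four further days give 6 × 7 = 42 variables per cycle, and separate models could make a patient a complete responder who also used rescue. The component imputations must also respect the overall complete response already imputed for the primary, or the mismatch is only moved.

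Cost: SAP wording, some extra programming and validation before database lock, and a protocol change, because SAP 2 declares no departures from the protocol. That change may need ethics and authority approval by country (protocol 4.2). No patients or new data are needed.
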